# Consenting non-English reading participants

For participants that are unable to read English, we will provide them a short form consent or full consent in the language they can read and ask them to sign. These participants will also be given a written summary/short form in English that has been signed by a study team member. A friend or family member (witness) that is fluent in both English and the participants language will be present and will translate the short form English consent for the participant. This witness will sign both the English and non- English forms and a copy of these signed forms will be given to the participant.

# Consent form signatures

English summary or long form English consent- signed by a study team member & witness Non-English short form or Non-English standard form consent- signed by participant & witness

Participant receives a signed copy of both forms. Study personnel retains all forms that were signed.

Consent forms available

Standard informed consents are available in English, Spanish, Albanian and Arabic Short forms are available in Chinese, French, Hindi, Korean, Igbo and Tagalog

Baseline screening examination: Screening examinations will take approximately 1 hour. The technician will contact UM registration to create a unique UM Medical Record Number (MRN) for each patient, which will be linked to their community clinic MRN through a secure spreadsheet. Images will be stored using the UM MRN on the secure UM ophthalmic imaging platform. If the patient is not currently a clinic patient, creating a patient record at Hope is not necessary, although creating a patient account at Hamilton is required.

## **Ophthalmology Technician Eye Exam:**

- (1) Health history
- (2) Vision exam for uncorrected and best- corrected visual acuity (UCVA and BCVA) at distance and near
- (3) Contrast sensitivity
- (4) Eyeglass evaluation including inter- pupillary distance
- (5) Eye exam testing including pupillary response, anterior chamber angle assessment by penlight, extraocular motility and alignment, and intraocular pressure measurement
- (6) Imaging of the posterior pole by fundus photography and Optical Coherence Tomography (OCT)

Technicians will have a "no dilation" protocol for patients with narrow angles by penlight or those with a history of glaucoma, an afferent pupillary defect, or intraocular pressure ≥ 21 mmHg. Previous community-based screening studies have had no cases of acute angle

closure glaucoma by following these recommendations. All other patients will be dilated prior to photography. Dilated participants will be instructed to return to the clinic if they should experience any headache, eye pain, redness or nausea after their examination. If a participant returns with any of these complaints, the technician will re-measure intraocular pressure. If IOP is elevated by >5mmHg over their pre-dilation measurement and >21mmHg, the technician will contact the ophthalmologist on call. Protocols exist for potentially urgent situations, including but not limited to: acute vision loss, flashes and floaters, severe eye pain, an afferent pupil defect, new onset double vision, or intraocular pressure measure ≥32 mmHg. The technicians will also be trained to contact the physician if they see abnormal findings on fundus photography, using the TECS training as a guide.

Upon dilation, fundus photographs and OCT images will be taken. The fundus photography protocol will be the validated protocol used for the VA diabetic tele-retinal screening program. Four photographs are taken: 1) an external photograph of the eye; 2) an image centered on the posterior pole; 3) an image centered on the optic nerve; and 4) an image centered on the supero-temporal arcade. Spectral-domain OCT will be used to obtain images of the retinal nerve fiber layer and ganglion cell layer of the macula. The UM software platform for storing and visualizing ophthalmic images will be utilized. The cameras will have software installed that facilitates all images being uploaded automatically to the imaging platform under the participant's UM MRN following HIPAA secure standards.

**Baseline Surveys**: For surveys, ophthalmic technicians will administer the National Eye Institute Visual Function Questionnaire – 9 to patients, which assesses vision-related quality of life. Additional surveys will include: Flint Water- questions are related to living in Flint during the water crisis, Everyday Discrimination Scale, Perceived Stress Scale, UCLA Loneliness Survey, Fall history and Timed Up & Go. They will also administer a standardized survey about socio-demographics and health history. Patients will confirm their address, phone number, and contacts in case of an emergency.

Eyeglasses: After the examination, ophthalmic technicians will help participants who need correction select free (ReSpectacle.org) or low-cost (ZenniOptical.com) eyeglass frames. ReSpectacle.org are donated glasses that have been categorized by exact prescription and are viewable on the website. The organization ships the glasses free- of charge. Participants may also purchase low cost (\$10-\$50) glasses on ZenniOptical.com. On this website, people can choose the frames. For both options, technicians will place the on-line order after the ophthalmologist confirms the eyeglasses prescription remotely, glasses will be shipped to the clinic.

Physician Evaluation: Physician's evaluation will be via a store-and-forward telemedicine technique. This store-and-forward technique, or asynchronous telemedicine, involves the electronic transmission of health data to the provider for evaluation and management. Physicians will review data received within 1 week. The reading ophthalmologist will enter the data into the UM EHR (MiChart). The physician will complete one of two letters with the examination results for the participant indicating whether the participant has ophthalmic disease or not. A time frame for an in-person ophthalmologist examination will be requested if needed. This letter will be sent to the patient via mail and the technician and the patient's PCP (if they have one) via the EHR.

**Physician Review Glaucoma Screen:** In terms of glaucoma screening, a "positive screen" for glaucoma or glaucoma suspect will include the following exam criteria as defined by the TECS protocol:

- 1) Cup to disc ratio  $\geq 0.7$
- 2) Intraocular pressure ≥ 21 mm Hg
- 3) Disc hemorrhage
- 4) Asymmetry of the cup-to-disc ratio by  $\ge 0.2$  where the larger cup-to-disc ratio is  $\ge 0.6$
- 5) Rim thinning or focal notch
- 6) Abnormal retinal nerve fiber layer observed on OCT defined as >10 microns difference in average retinal nerve fiber layer between the two eyes or the presence of thinning (defined as <5% or yellow) in any of the superior or inferior clock hours)
- 7) Narrow angles on penlight examination or any other concern for narrow angle (complaint of chronic headache or red eye)
- 9) Afferent pupillary defect
- 10) Patient already on treatment or being followed for glaucoma

Physicians will also evaluate for diabetic retinopathy and macular degeneration using validated TECS protocols. If the ophthalmologist identifies an urgent issue such as corneal ulcer, optic disc edema, melanoma, tumor, or retinal vascular event (e.g. central or branch retinal vein or retinal artery occlusion), the physician will contact the patient by phone to arrange immediate care.

Follow-up: The technician will schedule a follow-up visit 4-8 weeks later to give participants their eyeglasses and adjust them. Participants that do not need eyeglasses, but screen positive for eye disease, will return to review their diagnosis letter and management plan and help the patient to schedule an in-person appointment with the ophthalmologist. The ophthalmic technician will help the patient arrange follow-up care and provide educational material to explain diagnoses of cataract, diabetic retinopathy, macular degeneration or glaucoma. (UM Health System Patient Education Clearinghouse at https://pteducation.med.umich.edu/kellogg) If the participant has no need for eyeglasses and has no eye disease, the technician will call the participant to cancel the follow-up appointment after reviewing the ophthalmologist's recommendations. During the follow-up phone call, the satisfaction survey will be administered that would have otherwise been administered at the follow-up visit.

Glaucoma or glaucoma suspect: Patients with a diagnosis of glaucoma or glaucoma suspect who speak English will be randomized (1:1) to receive standard care as described above, or a 60-minute personalized counseling and education program (intervention) about their diagnosis and the importance of glaucoma follow-up care in maintaining vision (Aim 3)). Ocular hypertension that is low risk for developing glaucoma within one year and/or the recommended follow up time period is one year or more, will not be randomized, the PI will review these cases to determine if they should be randomized or not. Randomization will occur in web-based randomization system. Both groups will be provided support scheduling their ophthalmologist exam and will be asked to complete a brief satisfaction survey. The standard care group will receive a reminder call prior to the ophthalmologist exam, while the intervention will receive a

reminder call as well as a 10-15 minute motivational-interviewing based- counseling follow-up phone call to remind them of why following up for glaucoma care is important to them and trouble-shoot barriers to attending. Further discussion regarding personalized counseling and motivational interviewing can be found later in this protocol. All non-English speaking patients will not be randomized and will receive standard of care education; the personalized counseling is only available in English. We have created a Spanish version of the personalized counseling. Spanish speaking participants will not be randomized, all will receive the personalized coaching session. A Spanish speaking study coordinator will conduct the Spanish eHealth coaching. All subjects participating in the counseling/education encounters will have the option to have their sessions be audio-recorded. Additionally, we will ask English and Spanish speaking participants to complete a visual field test at this appointment. A visual field test measures peripheral vision and is used to review glaucoma patients. This test will take about 20 minutes and there will be no charge to the participant or their insurance. Visual field data will be entered into the REDCap database.

March 2024. Interviews have been completed; no further interviews will be conducted. Spanish speaking participants will be asked to participate in a post- coaching semi-structured interview to identify program components that are helpful/unhelpful and areas for improvement. Interviewers will follow the survey interview guide post-coaching interview guide and participants will receive a \$20 Visa gift card. Additionally, interviews will be recorded, transcribed, and stored on a secure UM server. Qualitative software such as Dedoose may be utilized.

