During the first day of training, counselors are taught to ask open-ended questions, or questions that cannot be answered with a "yes" or "no" response. They learn reflective listening, or para-phrasing what a person has said to ensure the person knows the counselor

is hearing and understanding what they say. They learn to use affirmations to praise actions people are taking towards improving their health and vision. They learn to use the elicit-provide-elicit technique to give information. This involves assessing people's knowledge prior to giving information, asking permission to give new information or advice, and then following up by eliciting the person's response to the new information in order to evaluate their understanding. This non-directive way of giving advice and information supports people's autonomy. During the second day of training, counselors are taught how to make complex reflections.

Complex reflections are statements that para-phrase what a person has said and adds significant meaning to help make a person think about the implications of their statement. Counselors learn how to promote change talk and develop an action plan to adhere to follow-up care recommendations.

Role playing is used to develop these skills using a video collection of glaucoma patients explaining their reasons for not engaging in their glaucoma management. The training consists of approximately 35% didactic material and 65% role-playing and interactive learning.

Primary outcome: The primary outcome will be adherence to the recommended follow-up appointment with the ophthalmologist within 6 months due to availability in scheduling these appointments. Six-month adherence will be used as the endpoint for all participants. Adherence in each treatment group will be calculated as the proportion of patients who attended the initial scheduled follow-up visit with an ophthalmologist as recommended after being diagnosed with glaucoma or glaucoma suspect on screening exam, dividing by the total number of patients diagnosed with glaucoma or glaucoma suspect during the screening exam and scheduled for follow-up with an ophthalmologist. This objective outcome variable will be assessed through record review by the study coordinator who is masked to the treatment allocation.

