# **Data Analysis**

Primary outcome: The primary outcome (attendance to follow-up appointment with a glaucoma specialist within three months) will be summarized with frequencies and percentages by intervention and control groups, overall and stratified by site.

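### The one-year cut-off for randomisation and the six-month adherence window do not match, so an on-time visit recommended after six months can count as non-adherence

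*Protocol*

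**What the plan says.** All references are to the protocol.

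- **Who is randomised.** The paragraph on glaucoma or glaucoma suspect, under Ophthalmology Technician Eye Exam, randomises English-speaking patients with either diagnosis 1:1. The only limit tied to the follow-up interval is that low-risk ocular hypertension and/or cases where "the recommended follow up time period is one year or more, will not be randomized". It adds that "the PI will review these cases to determine if they should be randomized or not".
- **How the interval is set.** Under Physician Evaluation, the reading ophthalmologist sets it for each patient: "A time frame for an in-person ophthalmologist examination will be requested if needed". The possible intervals and their frequencies are not given.
- **How the outcome is scored.** The Primary outcome paragraph under Research design-Intervention defines it as "adherence to the recommended follow-up appointment with the ophthalmologist within 6 months due to availability in scheduling these appointments", and adds: "Six-month adherence will be used as the endpoint for all participants". The numerator is those who "attended the initial scheduled follow-up visit with an ophthalmologist as recommended". The denominator is everyone diagnosed with glaucoma or suspect and scheduled for follow-up, whatever the recommended interval.
- **A different window elsewhere.** The Aim 3 Data Analysis section has "attendance to follow-up appointment with a glaucoma specialist within three months". The Aim 3 paragraph under Specific Aim/Hypothesis also says three months.
- **Status.** Planned Analysis Results Nov. 14, 2023 reports no difference in adherence between the arms and, for that reason, ends randomisation.

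**The concern.** The upper limit on the recommended interval at entry is twice the length of the scoring window. Take a patient asked to come back at nine months. The entry rule does not keep that patient out. The outcome rule puts the patient in the denominator and closes the window three months before the recommended date. A patient who does exactly what was asked is then counted as a failure.

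For such a patient the outcome no longer measures what it is named for, and the two halves of its definition (within six months, and as recommended) give opposite scores. Because the interval is set before randomisation, the effect is expected to fall equally on both arms. It should not favour either one, but it lowers both rates, shrinks the absolute difference and costs power. That bears on how firmly the reported absence of a difference can be read.

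**Working it through.** **1. Setting the rules side by side**

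| Recommended interval | Randomised? | Score if attended on the recommended date, six-month rule |
|---|---|---|
| Up to 6 months | Yes | Adherent |
| Over 6, under 12 months | Yes, by the stated rule | Non-adherent, although attended as recommended |
| 12 months or more | No by default; case review may admit | Non-adherent if admitted |

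Under the three-month wording the middle row becomes over 3 to under 12 months. The start of the window (screening, randomisation or referral) is not stated, so its edge is uncertain by the time between those events.

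**2. Inputs for the size**

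- From the protocol: 400 participants randomised 1:1, so 200 per arm. No alpha, power, adherence rate or effect size is given with it, so this figure cannot be reproduced. The number actually randomised when randomisation stopped is not given either.
- Assumed: two-sided 5%; control 50%, intervention 63.8%. This effect was picked because it gives about 80% power with 200 per arm.
- Assumed: a share f has an interval over 6 and under 12 months, and none of them attends within six months. An early visit would count as a success, so this is the worst case for a given f.

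**3. Formulas**

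Observed rates: p₁ = 0.50(1 − f) and p₂ = 0.638(1 − f). The difference is d = 0.138(1 − f). The ratio is 0.638/0.50 = 1.276 for every f.

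Power = Φ[(d − 1.96·SE₀)/SE₁], with p̄ = (p₁ + p₂)/2, SE₀ = √[2p̄(1 − p̄)/200] and SE₁ = √[p₁(1 − p₁)/200 + p₂(1 − p₂)/200].

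Example, f = 10%: p₁ = 0.450, p₂ = 0.5742, d = 0.1242, SE₀ = 0.04999, SE₁ = 0.04960. Then (0.1242 − 0.0980)/0.0496 = 0.53, and Φ(0.53) is about 0.70.

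**4. Results**

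| f | Observed rates | Difference (points) | Power, all 200 per arm | Power if restricted to 200(1 − f) per arm |
|---|---|---|---|---|
| 0% | 50.0% vs 63.8% | 13.8 | 80% | 80% |
| 5% | 47.5% vs 60.6% | 13.1 | 75% | 78% |
| 10% | 45.0% vs 57.4% | 12.4 | 70% | 76% |
| 20% | 40.0% vs 51.0% | 11.0 | 60% | 70% |
| 30% | 35.0% vs 44.7% | 9.7 | 51% | 65% |

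**5. Sensitivity to the assumed rates**

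With a 15-point effect and 200 per arm, power at f = 0, 5, 10, 20 and 30% is:

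- 40% vs 55%: 85, 82, 78, 70, 61%
- 50% vs 65%: 86, 82, 77, 67, 57%
- 60% vs 75%: 90, 85, 79, 67, 56%

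At f = 5% the loss is about 3 to 5 points across all these assumptions. It becomes material from about 10% upward.

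**The case against.** **No affected patient is shown.** The protocol never says that an interval between 6 and 12 months was recommended to anyone. The surrounding text points to shorter intervals: the window was three months in the aims, it became six because of appointment availability, and the counselling call comes two to six weeks after the session. This stands. The affected share may be close to zero.

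**The exclusion sentence is ambiguous.** It opens with ocular hypertension and joins the interval clause with and/or. This also stands, but it does not close the gap. If the clause covers ocular hypertension only, other suspects have no upper limit on their interval and the gap is wider.

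**The outcome could be read the other way.** Attendance as recommended might mean attendance by the recommended date, and the analysis plan, which is not available here, may settle the scoring. But the protocol states six months for all participants in the same paragraph. An abstractor has to pick one rule, and the two conflict.

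**A uniform window is a legitimate choice.** It is objective, assessed by masked record review and the same in both arms. This stands, and it is a reason to keep it as the primary result.

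**Stronger readings.** A reader might infer that compliant patients were in fact misclassified, that patients beyond the window could never succeed, or that dilution explains the null result. The documents support none of these: f is unknown, an early visit would count, the ratio is unaffected, and no adherence figures by arm are given.

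**Conclusion.** The mismatch between the entry cut-off and the scoring window is in the text, and it contradicts the outcome's own definition. It follows from stated rules and is not a matter of missing detail. Its effect is limited to patients with a recommended interval over 6 and under 12 months, plus any with longer intervals admitted on review. Nothing in the protocol shows how many of them there were.

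The size is therefore conditional. It rests on the assumed rates, on 200 analysed per arm, and on no one in the group attending early. On that basis the loss of power runs from about 5 points at f = 5% to about 29 points at f = 30%. The expected effect is a smaller absolute difference, with no systematic advantage to either arm. The finding calls for clarification and a supporting analysis. It does not show that the reported result is wrong.

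**What to change.** 1. Reconcile the four places that bear on this: the Aim 3 paragraph under Specific Aim/Hypothesis, the randomisation rule for glaucoma or glaucoma suspect, the Primary outcome paragraph, and the Aim 3 Data Analysis section. State one window and when it starts, and how a visit recommended after its end is scored.
2. Keep six-month attendance in all randomised participants as the primary result. The result is already known, so replacing the definition or dropping randomised participants from the primary set would be a post hoc change of endpoint.
3. Report, by arm, the share with a recommended interval beyond six months.
4. Add one supporting analysis, labelled as added after the November 2023 result. Either score attendance by each participant's recommended date plus one fixed allowance common to both arms, or restrict to recommended intervals of six months or less. The interval is set at the remote reading, before randomisation at the return visit, so either option keeps the arms comparable.
5. Qualify the conclusion of no difference in the light of items 3 and 4.

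**Cost.** The follow-up plan in the physician's letter is already entered into REDCap (Recording of Data), so little new data is needed. Scoring by individual date needs longer record review for those with late dates; the restricted set is smaller. In either form the added analysis is post hoc and can only support the primary result.

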## Planned Analysis Results Nov. 14, 2023

A planned analysis reported no difference in adherence between the intervention (personal coaching) and the control (standard education). Therefore, we will no longer randomize glaucoma/glaucoma suspect participants and instead ask them to choose which education they would like to receive.

**Follow-up surveys:** All returning participants will complete a satisfaction survey. The intervention group will also be asked to complete; 1) National Eye Institute Glaucoma Eye-Q test, 2) Satisfaction with Information Scale, 3) Clinician and Group Survey of the Consumer Assessment of Healthcare Providers and Systems (CG- CAHPS), 4) Health-Care Climate- eye care (HCCQ), 5) Confidence in question asking, which will be assessed with the following question "How confident are you in your ability to know what questions to ask the ophthalmologist?" and will have responses ranging from 1-10 on a Likert scale where 1 is "not confident at all" and 10 is "extremely confident."

Follow-up Care with an Ophthalmologist: The ophthalmologists who remotely reviews the screening examination data will make recommendations follow-up care. All patients who screen positive for ophthalmic disease will be referred to the comprehensive ophthalmologist at the Hamilton Clinic, or to the Hope-Kellogg ophthalmology clinic that runs every two months on a Saturday. The comprehensive ophthalmologists will either provide definitive care or provide a referral for further sub-specialty care. If the patient has barriers to accessing sub-specialty care at the Hamilton clinic, social workers and financial counselors will be involved to help with logistical barriers. If a patient from Hamilton clinic

has moderate or severe glaucoma, they can be referred to see the glaucoma specialist from UM who will have one day of clinic per month at Hamilton Clinic. If a patient from Hope requires further specialty consultation or surgery, they will sign up for MSupport, the UM charity care program, with the financial counselor available on-site during the Saturday clinics. Once a patient receives MSupport, they receive free care and medications at the UM for 12 months with the option to renew the services annually with proof of low income. Once a patient receives MSupport, they will be scheduled with the appropriate provider at the UM. For participants that are glaucoma/glaucoma suspect and seen at Hamilton or the Kellogg Eye Center for their follow up exam, these findings and visual field data will be collected and entered into the REDCap database.

One-Year Vision Outcomes: Repeat screenings at one year following the participants initial enrollment will take place during the second and third year of the program, where phone calls will be made to participants screened in the first or second year of the program (regardless if they screened positive or negative for disease) to encourage them to return for a second screening. When they return, they will follow the same protocol as described for the initial visits with the ophthalmic technician above. Although, One-Year visit survey data will only include demographics and the VFQ-9 and Falls survey which they also completed in their initial enrollment. Participants who were already randomized to the clinical trial in Aim 3 will not be re-randomized.

**Two-Year Vision Outcomes**: Repeat screenings will take place during the third year of the program, where phone calls will be made to all participants screened in the first year (regardless if they screened positive or negative for disease) to encourage them to return for a second screening. When they return, they will follow the same protocol as described for the initial visits with the ophthalmic technician above. Participants who were already randomized to the clinical trial in Aim 3 will not be re-randomized.

Participants that do not return to the clinic for a repeat screening examination, will be asked to complete the VFQ-9 survey over the phone when they are contacted.

One and Two-Year Vision Outcomes: These participants will need to meet the inclusion/exclusion criteria listed in section Recruitment Section of this protocol.

**Post Program Participant Interview:** We will ask up to 75 participants to participate in a post program interview to identify program components that are helpful/unhelpful and areas for improvement. We will randomly contact English speaking participants within our study database that agreed to be contacted for future studies. The study consent document contains an additional signature section for participants to consent/not consent contact for future research. Selected participants will be contacted by phone, or in-person following their last appointment. Interviewers will follow the survey interview guide. Interviews will be conducted via in-person at the clinics, telephone, or UM Zoom. Participants will receive a \$20.00 Visa Gift Card or check by mail or in-person. Additionally, interviews will be recorded, transcribed, and stored on a secure UM server. Qualitative software such as Dedoose may be utilized. 1/24/2023 English post program interviews have been completed.

**Evaluation of "No-show" Appointments:** We will evaluate our high (approximately 35%) no-show and last-minute cancelations rates at this community clinic study (Hope & Hamilton

Community Clinic). The SIGHT study is open to non- clinic patients, therefore, potential participants may or may not be clinic patients. We will only review data of the SIGHT study "no shows" and will not include the clinics appointment "no shows". When potential participants contact the SIGHT team, the team member reviews the recruitment script that describes the study. Following this discussion and verification of study eligibility, a medical record number (MRN) in MiChart is created for those that do not already have an MRN. The SIGHT study baseline appointment is then made within the MiChart system. This process is completed prior to consent.

It may be possible that high no-show rates are associated with lack of convenient transportation. By accessing patient information for those that missed appointments, we can investigate the logistical barriers of cost and transportation for show versus no-show patients. Associations between outcome variable (shows versus no-shows) and demographics, including age, sex, and race, zip codes and logistical factors such as cost, travel time, and distance from appointment location will be studied graphically (e.g., boxplots and scatterplots) and with appropriate inference tools (e.g., t-tests, chi-square tests, regression) where available. This will be completed by utilizing the potential participants medical record number access the described variables where available. Additionally, when available, reasons given by the potential participant to the SIGHT team for "no-shows" and last-minute cancellations will be analyzed.

